### ***Handling of adverse events/hypoglycemia with missing or partial date/time of onset***

Missing or partial missing AE/hypoglycemia onset dates and times will be imputed so that if the partial onset date/time information does not indicate that the AE/hypoglycemia started prior to treatment or after the treatment-emergent period, the AE/hypoglycemia will be classified as treatment-emergent. No imputation of AE end dates/times will be performed. These data imputations are for categorization purpose only and will not be used in listings. No imputation is planned for date/time of AE resolution.

### ***Handling of adverse events/hypoglycemia when date and time of first IMP administration is missing***

When the date and time of the first double-blind IMP administration is missing, the day of randomization should be considered as the start date of TEAE period. The exposure duration should be kept as missing.

### ***Handling of adverse events/hypoglycemia when IMP end of treatment date is missing***

For the purpose of defining TEAE period, the date of the last administration of IMP is equal to the date of the last administration reported on the eCRF “Treatment Status” page.

If the date of last administration reported on the eCRF “Treatment Status” page is

- Partially missing, it will be imputed with a date as late as possible before or on the date of last available information on eCRF “Completion of End of Study/Follow-up”.
- Completely missing, it will be imputed with the date of last available information on eCRF “Completion of End of Study/Follow-up” page.

If the date of last available information on eCRF “Completion of End of Study/Follow-up” page is

- Partially missing, it will be imputed with a date as late as possible.
- Completely missing, all adverse events occurred on or after the first administration of double-blind IMP will be considered as treatment emergent adverse events.

### ***Handling of missing assessment of relationship of adverse events to IMP/NIMP/study procedures***

If the assessment of the relationship to IMP/NIMP/study procedures is missing, the relationship to IMP/NIMP/study procedures has to be assumed and the AE considered as such in the frequency tables of possibly related AEs, but no imputation should be done at the data level.

### ***Handling of missing severity/grades of adverse events***

For a patient and a preferred term, if the severity is missing for one of the treatment-emergent occurrences of an AE, the maximal severity on the remaining occurrences for the patient and the preferred term will be considered. If the severity is missing for all the occurrences, a “missing” category will be added in summary table.

### ***Handling of potentially clinically significant abnormalities***

If a patient has a missing baseline he will be grouped in the category “normal/missing at baseline.”

For PCSAs with 2 conditions, one based on a change from baseline value or a normal range and the other on a threshold value, with the first condition being missing, the PCSA will be based only on the second condition.

For a PCSA defined on a threshold and/or a normal range, this PCSA will be derived using this threshold if the normal range is missing; eg, for eosinophils the PCSA is  $>0.5$  GIGA/L or  $>ULN$  if  $ULN \geq 0.5$  GIGA/L. When ULN is missing, the value 0.5 should be used.

Measurements flagged as invalid by the laboratory will not be summarized or taken into account in the computation of PCSA values.

## 2.5.4 Windows for time points / Measurements for analyses

For statistical analyses on efficacy, PRO questionnaires (WRSM, APPADL and IW-SP), a scheduled measurement will be used if it is available, regardless of treatment discontinuation or initiation of rescue therapy. An unscheduled measurement will be allocated to a post-baseline visit based on the study day that the unscheduled measurement is taken. An allocation is performed only if there is no scheduled measurement for the visit to be allocated to. However, if the unscheduled measurement (central laboratory measurement only for laboratory data) is taken on the same date of the scheduled visit, the value will be used in the analyses, regardless whether or not there is a scheduled measurement for the visit.

**Table 4 - Allocating an unscheduled measurement to a post-baseline visit**

Unscheduled measurement taken in study days a	Visit to be allocated to	Targeted study day for the visit
2 - 20	Visit 6 (Week2)	14
21 - 41	Visit 8 (Week 4)	28
42 - 76	Visit 9 (Week 8)	56
77 - 118	Visit 10 (Week 14)	98
119 - 160	Visit 11 (Week 20)	140
≥161	Visit 12 (Week 26)	182

a Study days are calculated from the day of first IMP injection; the day of first IMP injection is Day 1.

If more than one measurements are allocated to a visit, the one closest to the targeted study day (as shown in table above) will be used. Furthermore, if there are more than one measurement that are equally close to the targeted study day but measured on two different dates, measurements from the later date will be used. If there are more than one measurement taken on the same date, the average will be used.

The premature treatment discontinuation visit is entered in the eCRF if a patient prematurely discontinues treatment. These measurements will be allocated to a scheduled visit using the same criteria described above.

Pre-rescue therapy visit is entered in the eCRF if a patient receives rescue therapy. These measurements will also be allocated to a scheduled visit using the same criteria described above.

Furthermore, end of treatment visit measurements from patients prematurely discontinue the study (“Subject Status” in “Completion of End of Study/Follow-up” page is not “Completed”) will also be allocated to a scheduled visit using the same criteria described above.

Similar criteria of allocating an unscheduled measurement to a scheduled visit will be used for safety variables (laboratory variables, vital sign, ECGs, holter monitor variables), including measurements from premature treatment discontinuation visit, pre-rescue therapy visit, and end of treatment visit for patients prematurely discontinue the study if any. However, descriptive statistics, PCSA analyses, and shift summaries for safety variables are based only on data from TEAE period, a detailed definition of the TEAE period is provided in [Section 2.1.4](#).

After allocation, if there is still no measurement for a given parameter at a scheduled visit, multiple imputation would be applied efficacy and PRO questionnaires as described in [Section 2.4.4](#) and [Section 2.4.9](#).

### ***Baseline definition for efficacy/safety data***

For the safety analyses, the baseline for a given parameter is defined as the last available measurement, including unscheduled assessments, assessed prior to the first administration of IMP. For the efficacy analyses, the baseline for a given parameter is defined as the last available measurement, including unscheduled assessments, assessed prior to the first administration of IMP or the last available value on or before the date of randomization if not treated with IMP.

### ***Summary statistics by visit for continuous efficacy endpoints and PRO questionnaires (WRSM, APPADL and IW-SP)***

Summary statistics (N, mean, SD, SE, minimum, median, maximum) of continuous efficacy endpoints (observed data and change from baseline) will be provided at scheduled visits as per protocol. Summaries showing data by visit will be presented according to the visit number (or re-allocated visit number) and labeled with the targeted week. The analyses will be based on data after applying the allocation of measurements from unscheduled visit, premature treatment discontinuation visit, pre-rescue therapy visit, and end of treatment visit as described above in this section.

### ***Last on-treatment value for safety variables (laboratory variables, vital sign, ECGs, holter monitor variables)***

The last on-treatment value is the final measurement assessed during treatment epoch for safety variables, regardless of the introduction of rescue therapy, including measurements at unscheduled visits. The definition of treatment epoch is provided in [Section 2.1.4](#), also see details in [Section 2.4.5](#).

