- ^a In case of rescue therapy, all assessments planned in V12 should be performed before starting rescue therapy, patients then continue the study treatment (including metformin), and all visits and assessments should be performed as scheduled. In case of premature permanent IMP discontinuation, patients should have a visit as soon as possible with the assessments normally planned in V12 (the standardized meal test and PK collections are performed only if the patient receives the IMP the day of the visit, note that otherwise predose PK sample can be taken if the patient receives the IMP the day before). Afterward, the patients should continue in the study up to the scheduled date of study completion. They should be followed up according to the study procedures as specified in the protocol (except for the 3 day safety post-treatment and PK assessment). If the patient drops out from the study at the time of IMP discontinuation regardless if the patient receives the IMP or not on the day of the meal test, the meal test should be performed. However, PK collections are performed only if the patient receives the IMP the day of the visit, otherwise predose PK sample can be taken if the patient receives the IMP the day before.
- ^b Weight will be recorded to the nearest 0.1 kg and should be measured using calibrated scales. The same pair of scales should preferably be used throughout the trial. Weight should be measured in the fasting state in the morning at approximately the same time with an empty bladder, without shoes and only wearing undergarments or light clothing. Weight measured at screening Visit 1 will be used only for calculation of screening BMI for eligibility criteria whereas weight measured at Visit 4 will be used as baseline for assessment of change in body weight and for calculation of baseline BMI which will be the BMI value used for stratification.

- c* At Visit 9, abbreviated/targeted physical examination only.
- d* Diary will be reviewed at each on site visit.
- e* Counseling will be provided at screening Visit 3 or Visit 4.
- f* Only for patients in SAR425899 or Placebo arms.
- g* First dose of IMP will be done on-site .IMP administration every day along the 26-weeks, but at each visit on site, the IMP administration will be done on site by the patient himself.
- h* 7-point profile to be conducted over a single 24-hour period in the week before Visit 4, Visit 10 and Visit 12.

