9.2.2.1 Observation period of safety endpoints

The observation period of safety data will be divided into 3 segments:

- The pretreatment period is defined as the time between the date of the informed consent and the first injection of IMP.
- The on-treatment period is defined as the time from the first injection of IMP up to 3 days (1 day for hypoglycemia) after the last injection of IMP, regardless of the introduction of rescue therapy. The 3-day interval is chosen based on the half-life of the IMP (approximately 5 times the half-life of SAR425899).
- The post treatment period is defined as the time starting 4 days after last injection of IMP (after the on-treatment period).

The baseline value for safety endpoints will be the last available value prior to the first injection of IMP.

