10.3.3 List of criteria for permanent treatment discontinuation

The patients may withdraw from treatment with the IMP if they decide to do so, at any time and irrespective of the reason, or this may be the Investigator's decision. All efforts should be made to document the reason(s) for treatment discontinuation and this should be documented in the eCRF.

Patients may withdraw from treatment with IMP in case of the following reasons:

- At patient's own request, ie, withdraw of consent for treatment.
- If, in the investigator's opinion, continuation with the administration of IMP would be detrimental to the patient's well-being.
- At the specific request of the sponsor.

A patient must withdraw from treatment with IMP in case of the following:

- Intercurrent condition that requires discontinuation of IMP: eg, laboratory abnormalities (see decision tree and general guidance for the follow up of laboratory abnormalities in [Appendix C](#)), diagnosis of acute pancreatitis confirmed by gastroenterologic evaluation and imaging (see [Section 10.6.4](#)), calcitonin value ≥ 50 pg/ml (see [Section 10.6.6](#)).
- Pregnancy.
- Systemic hypersensitivity reaction.

Any code-breaking requested by the Investigator will lead to permanent treatment discontinuation.

Any abnormal laboratory value or ECG parameter will be immediately rechecked for confirmation (eg after 24 hours) before making a decision of permanent discontinuation of the IMP for the concerned patient.

Handling of patients after permanent treatment discontinuation

Patients will be followed-up according to the study procedures specified in this protocol up to the scheduled date of study completion, or up to recovery or stabilization of any AE to be followed-up as specified in this protocol, whichever comes last.

If possible, and after the permanent discontinuation of treatment, the patients will be assessed using the procedure normally planned for the last dosing day with the IMP including a pharmacokinetics sample if already scheduled.

All cases of permanent treatment discontinuation should be recorded by the Investigator in the appropriate pages of the eCRF when considered as confirmed.

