11.4.3 Analyses of safety data

The summary of safety results will be presented by treatment group.

All safety analyses will be performed on the safety population as defined in [Section 11.3.2](#) using the following common rules:

The baseline value is defined as the last available value prior to the first injection of IMP.

The following definitions will be applied to laboratory parameters, vital signs and ECG.

- The potentially clinically significant abnormality (PCSA) values for clinical laboratory tests, vital signs and ECG are defined as abnormal values considered medically important by the Sponsor's Global Pharmacovigilance and Epidemiology department and in effect at the time of the final statistical analysis plan approval. Potentially clinically significant abnormality criteria for parameters not cited in the protocol as safety parameters will not be analyzed.
- Potentially clinically significant abnormality criteria will determine which patients had at least 1 PCSA during the on-treatment period, taking into account all evaluations performed during the on-treatment period, including unscheduled or repeated evaluations. The number of all such patients will be the numerator for the on-treatment PCSA percentage.

The "observation period" defined in [Section 9.2.2](#) are applicable for classification of AEs, determination of on-treatment PCSA values and the last on-treatment value for the laboratory, vital sign and ECG parameters.

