#### *Observation period*

The observation period will be divided into 4 epochs:

- The **screening** epoch is defined as the time from the signed informed consent date up to the first administration of the IMP.
- The **treatment** epoch is defined as the time from the first administration of the IMP to the last administration of the IMP
- The **residual treatment** epoch is defined as the time from the last administration of the IMP up to 3 days (1 day for hypoglycemia, 28 days for anti-SAR425899 antibody) after the last administration of IMP.

The treatment-emergent adverse event (TEAE) period will include both **treatment** and **residual treatment** epochs.

- The **posttreatment** epoch is defined as the period of time starting the day after the end of the treatment-emergent adverse event period up to the end of the study (defined as last protocol-planned visit or the resolution/stabilization of all serious adverse events (SAE) and adverse events with prespecified monitoring as defined in protocol).

The on-study observation period is defined as the time from the start of treatment until the end of study (defined as the last scheduled visit for those who completed the study and the date collected on e-CRF page “Completion of End of Study/Follow-up” for those who did not complete the study, or the resolution/stabilization of all serious adverse events and adverse events with prespecified monitoring as defined in the protocol whichever is the latest).

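### The SAP ends the last on-treatment value for safety variables at the last injection, while the protocol runs it to 3 days after; one descriptive row is affected

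*SAP*

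**What the plan says.** **Protocol.** Section 9.2.2.1 sets the window, and its closing words refer to the final injection: "The on-treatment period is defined as the time from the first injection of IMP up to 3 days (1 day for hypoglycemia) after the last". It gives a pharmacokinetic reason: "The 3-day interval is chosen based on the half-life of the IMP (approximately 5 times the half-life of SAR425899". Section 11.4.3 says that the safety observation period applies to "determination of on-treatment PCSA values and the last on-treatment value for the laboratory, vital sign and ECG parameters".

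**SAP.** Section 2.1.4 splits the same span in two. For the part on treatment, it says that the "epoch is defined as the time from the first administration of the IMP to the last administration of the IMP". A separate residual part comes next, for which the "epoch is defined as the time from the last administration of the IMP up to 3 days (1 day for hypoglycemia, 28 days for anti-SAR425899"; the 28 days concern antibodies only. The two parts together form the TEAE period. Section 2.5.4 then ties the last on-treatment value to the first part only: "The last on-treatment value is the final measurement assessed during treatment epoch for safety variables, regardless of the introduction of rescue therapy".

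**Visits after early stopping.** Footnote a of the protocol flow chart says: "In case of premature permanent IMP discontinuation, patients should have a visit as soon as possible with the assessments normally planned in V12". Section 10.3.3 adds that, if possible, "after the permanent discontinuation of treatment, the patients will be assessed using the procedure normally planned for the last dosing day with the IMP".

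**The concern.** The two documents give different end points for the same quantity, and the SAP does not say that it meant to change it. Neither the protocol-change table in SAP 1.5 nor the SAP-change table in SAP 1.6 mentions it.

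The SAP is also uneven within itself. Its PCSA, shift and by-visit safety summaries use the TEAE period, and SAP 2.1.4.3 counts a death as on-treatment if it falls in the TEAE period. SAP 2.5.4 puts the last on-treatment row in the same tables as the by-visit rows, so one row would follow a narrower window than the rows above it.

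A last on-treatment row is useful mainly for patients who do not reach Week 26. For some of them the SAP wording passes over the reading taken when they stopped and shows an older one. Heart rate by ECG and Holter is part of a main secondary objective, so a reader is likely to look at this row.

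**Working it through.** **1. The windows side by side.** No half-life is stated. Taking the protocol's 3 days as 5 half-lives gives 72 h / 5 = 14.4 h. The share of drug remaining after d days is 0.5^(24d / 14.4).

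| Days after last injection | Drug remaining | Protocol on-treatment | SAP TEAE period | SAP last on-treatment value |
|---|---|---|---|---|
| 0 | 100% | in | in | in |
| 1 | 31% | in | in | **out** |
| 2 | 10% | in | in | **out** |
| 3 | 3% | in | in | **out** |
| 4 | 1% | out | out | out |

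The documents differ on days 1, 2 and 3 only. Day 0 is counted as inside because SAP 2.4.3.2 explains the treatment epoch by dates, and SAP 2.5.3 takes the date of last administration from the eCRF.

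**2. Can readings fall on days 1 to 3?** Yes. The flow chart and Protocol 10.3.3 place the discontinuation assessments at or after stopping, with no fixed day. Footnote a of the flow chart makes PK provision for a patient whose last dose was the day before that visit. Supine heart rate (Protocol 9.2.2.5) and the 12-lead ECG (9.2.2.6.1) are taken before the dose. A patient who injects one morning, attends the next and is not dosed again therefore has a day 1 reading. The interval since the last injection is about the same as for a routine scheduled reading, yet the SAP row excludes it.

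**3. How old is the replacement?** Post-baseline 12-lead ECGs are scheduled at Weeks 4, 14 and 26 only. Assuming no unscheduled ECG:

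- Stop at Week 13: the Week 4 ECG is used, 13 − 4 = 9 weeks before stopping.
- Stop at Week 25: the Week 14 ECG is used, 25 − 14 = 11 weeks before stopping.
- Stop before Week 4: no last on-treatment ECG.

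Vital signs are scheduled at Weeks 2, 4, 8, 14, 20 and 26. The longest interval is 6 weeks, so those gaps are shorter.

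**4. Where do the excluded readings still count?** They count in the PCSA and shift summaries, which use the TEAE period. They count in the by-visit summaries if SAP Table 4 allocates them. Example: last injection on Day 175 (Week 25) and ECG on Day 177. With no scheduled Week 26 ECG, Table 4 sends Day 177 to Week 26, because every day from 161 on goes there. The reading then stands in the Week 26 row, while the same patient's last on-treatment ECG is Week 14 (Day 98; (175 − 98) / 7 = 11 weeks before the last injection).

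**5. How many patients?** Number affected = early stoppers × share whose latest reading falls on days 1 to 3. The documents give neither factor. If 10% to 25% of a 60-patient arm stopped early (an assumption with no source in the documents), there would be 0.10 × 60 = 6 to 0.25 × 60 = 15 early stoppers. That is a ceiling, not an estimate of those affected.

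**The case against.** Several things limit the point.

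- **Only one descriptive row is touched.** SAP 2.4.5 calls the safety analysis essentially descriptive with no systematic testing, and the heart rate endpoint is the change to Week 26. This stands. A reader might infer that the readings are lost from the safety analysis; they are not.
- **For intolerance, assessment is written before stopping.** Protocol 8.1.1 lists the end-of-treatment assessments first and discontinuation second, so some readings fall on the last dosing day and are kept. This stands in part. Because ECG and heart rate are taken before the dose, it does not help a patient who attends the day after the last injection and is not dosed again.
- **Holter.** A reader might infer that a completer's Week 26 recording, which runs from the Visit 12 dose to 24 h later, lies wholly outside the epoch and that Week 14 becomes the last on-treatment value. The SAP does not support this. It treats the epoch by date, and the recording starts on the dosing day. Protocol 11.4.3 does not name Holter in its observation-period sentence, although 11.4.3.5 summarizes a last on-treatment Holter value. What remains is that the SAP does not say how to date a recording that runs into the next day.
- **Direction of bias.** A reader might infer that the row understates the change most at the higher doses. The documents do not show this. They give no stopping rates by dose, and with about 10% and 3% of drug left on days 2 and 3, a late reading may itself show a smaller effect than the older reading it would replace.
- **A drafting slip.** SAP 1.6 covers major changes, so the silence may mean that no change was intended. That is plausible, and it favours correcting the wording.

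**Conclusion.** The conflict is explicit and undeclared. Protocol 9.2.2.1 and 11.4.3 include days 1 to 3 after the last injection in the last on-treatment value for laboratory, vital sign and ECG parameters; SAP 2.5.4, read with 2.1.4, excludes them. Followed as written, the SAP replaces some readings that the protocol counts as on-treatment with older ones, or with none.

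The size is modest. A reading on the day of the last injection, or more than 3 days after it, is treated alike under both documents. A completer dosed at Visit 12, as the flow chart plans, keeps the Visit 12 readings. The number affected cannot be computed and is bounded above by the number of early stoppers; the 6 to 15 of 60 shown above is that bound under an assumed rate. The 9 to 11 week gaps are examples that apply to the 12-lead ECG when no unscheduled tracing exists. The 14.4 h half-life and the washout percentages rest on the protocol's approximate statement of 5 half-lives. The point is worth correcting because the tables would otherwise use two windows without saying so.

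**What to change.** In SAP 2.5.4, define the last on-treatment value as the last measurement in the TEAE period, from the first injection to 3 days after the last. State the 3 days explicitly, because the residual epoch has other lengths for hypoglycemia and antibodies. As a clarification only, add that a Holter recording started on the Visit 12 dosing day counts as Week 26 and as on-treatment. If the narrower window is intended, list it in SAP 1.6 with a reason.

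The cost is a sentence or two of wording and no new data. The downside is that a few values will come from up to 3 days after the last dose, with partial washout, which the protocol already accepts as on-treatment.
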